6.6 Follow-up

Patients discharged before full course of study drug is given (two postoperative doses) will be instructed to take study drug at home as outlined on patient instruction card, specifically: Patients discharged on day of surgery will take two doses at home (on day 0 and day 1 postop); patients discharged on day 1 postop will take one dose at home; and patients discharged after day 1 postop will not take any study drug. Patients will be advised to discard remaining study drug.

As part of standard of care, it is routine for nursing staff at MMP NSS to follow up with patients via phone call within 24 hours of discharge. As a part of this call, all study patients will be queried on any issues related to urinary retention. They will also be asked if they have continued their study medication as instructed.

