2.0 Background

In the United States, estimates of POUR rates range from 2% to 70%[1, 2]. This wide range is due to multiple factors affecting its incidence, including anesthetic regimen, duration and type of surgery, age, gender, co-morbidities and presence of pre-operative urinary symptoms[2]. There is a paucity of literature specific to spine patients, but published rates in this population range from 5% to 38%[3-5]. POUR can be painful, physically damaging, and emotionally troubling for patients.

Up to 22% of patients that develop POUR receive an intra-urethral catheter[6], which places them at an increased risk of developing hospital-acquired urinary tract infections. These catheter-associated urinary tract infections (CAUTIs) significantly contribute to patient morbidity, increase the average length of hospital stay, and are associated with increased inpatient mortality[2, 7]. CAUTIs also have a significant financial impact, costing U.S. hospitals an estimated \$400 million annually[8]. This is especially significant since the Centers for Medicare and Medicaid no longer compensate hospitals for the additional cost of treating CAUTIs, believing them to be reasonably preventable[9].

The exact pathogenesis of POUR is not well understood. One theory is that over-activation of alpha-adrenergic nerve receptors on the human bladder is an important contributor to urinary retention after surgery[10]. This theory is based on current understanding of bladder physiology and the fact that many agents such as ephedrine used during general anesthesia have activity at alpha-adrenergic receptors. Patients treated with ephedrine have been shown to be at increased risk of developing urinary retention [11, 12].

Tamsulosin, a medication that blocks these alpha-adrenergic receptors, has been shown to significantly reduce the incidence of POUR in specific surgeries when given preoperatively[13-15]. This drug, which is FDA approved and widely used to treat symptoms of bladder outlet obstruction and benign prostatic hypertrophy (BPH) in males, has a favorable side effect profile and a half-life of 9-15 hours, achieving steady state after 5 days with daily dosing[16]. While previous studies have demonstrated the practicality, efficacy, and safety of prophylactic tamsulosin for POUR, the trials were small and only examined urinary retention in patients undergoing hernia repair and other general surgical procedures; no spinal surgery patients were included in these trials.

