3.2 Secondary Objectives

Secondary analyses will include

- Treatment difference in length of stay
- Treatment difference in time to first spontaneous void

- Relationship between preoperative post-void residual (PVR) and POUR
- Correlation of baseline IPSS and POUR
- Relationship between duration of surgery and POUR

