9.1 Side Effects of tamsulosin

Specific side effects of tamsulosin and their reported frequency are[16] :

Greater than 10%:

- Orthostatic hypotension (first dose: 6% to 19%; symptomatic orthostatic hypotension (chronic therapy) <1%)
- Headache (19% to 21%), dizziness (15% to 17%)
- Ejaculation failure (8% to 18%)
- Infection (9% to 11%)
Rhinitis (13% to 18%)

1% to 10%:

- Drowsiness (3% to 4%), insomnia (1% to 2%), vertigo (\leq 1%)
- Loss of libido (2%)
- Diarrhea (6%), nausea (4%)
- Weakness (8% to 9%), back pain (7% to 8%)
- Blurred vision (\leq 2%)
- Pharyngitis (6%), cough (3% to 5%), sinusitis (4%)

Less than 1% (Limited to important or life-threatening):

- Epistaxis, exfoliative dermatitis, hypersensitivity reaction, hypotension, intraoperative floppy iris syndrome (IFIS), palpitations, priapism, syncope

With the exception of IFIS, all of these potential side effects are reversible. These and all other adverse effects, expected and unexpected, will be documented and reported.

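### The only stated post-discharge contact is timed from discharge, so for early discharges no stated contact asks about adverse events after the last home dose

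*Combined protocol and SAP*

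**What the plan says.** **Dosing.** Section 4.0 has study drug taken in the evening, with the last dose on postoperative day 1. Section 6.6 sends early discharges home with the doses still due: "Patients discharged on day of surgery will take two doses at home (on day 0 and day 1 postop"; and "patients discharged on day 1 postop will take one dose at home".

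**Contact.** Under 6.6 the office nurses routinely "follow up with patients via phone call within 24 hours of discharge". On that call "all study patients will be queried on any issues related to urinary retention", and patients are asked whether they kept taking study drug. No other topic and no later contact is stated.

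**Safety.** Section 3.1 makes the absence of added adverse-event risk part of the primary objective. Section 9.1 says of side effects: "These and all other adverse effects, expected and unexpected, will be documented and reported". Section 9.2 counts serious adverse events, readmission among them, over a study period with no defined end.

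**Other sources.** Section 10.1 adds office, bedside and Epic chart data, with no end date. Section 6.2 gives patients a diary card for doses but does not describe its return.

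**Related outcomes.** Section 3.2 lists "Treatment difference in length of stay". Section 4.0 closes the primary endpoint at the earlier of first spontaneous void and catheterization. Section 8.1 defines POUR by catheterization or re-catheterization and sets no time limit.

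**The concern.** The call is counted from discharge, whereas the last dose is fixed by the date of surgery. The earlier a man leaves, the more likely the call is to come before he has finished treatment. For a typical same-day discharge it cannot establish whether the seventh dose was taken or what followed it.

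The stated topics also omit adverse events in general. Section 9.1 lists effects such as dizziness (15% to 17%), which a man at home may never report to anyone who writes in the Epic chart.

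At stake is the safety half of the primary objective. How long adverse events are actively looked for depends on length of stay, which is determined after randomization and which the trial compares between arms.

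**Working it through.** The plan gives no figure for its observation window, so there is none to reproduce. Its sample size (264 per group for 17.0% versus 8.5%, two-sided 0.05, 80% power, continuity-corrected) reproduces exactly and is not affected.

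**Inputs from the documents:** evening dosing ending on day 1 (4.0); call within 24 hours of discharge (6.6); "half-life of 9-15 hours" (2.0).

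**Assumptions:** all clock times, and five half-lives as washout. The documents do not give the share of men discharged on day 0 or day 1.

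**1. Day 0 discharge.** Let H be the discharge hour and D the dosing hour. The latest call is at hour H on day 1, so it precedes the last dose by D − H hours.

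| H | D = 18:00 | D = 20:00 | D = 22:00 |
|---|---|---|---|
| 12:00 | 6 h before | 8 h before | 10 h before |
| 14:00 | 4 h before | 6 h before | 8 h before |
| 16:00 | 2 h before | 4 h before | 6 h before |
| 20:00 | up to 2 h after | same time | 2 h before |

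The call can follow the dose only when H is later than D.

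**2. All discharge days, 21:00 dose on day 1.** Time from last dose to latest call:

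| Discharge | Latest call | Relative to last dose |
|---|---|---|
| Day 0, 17:00 | Day 1, 17:00 | 17 − 21 = −4 h |
| Day 1, 12:00 | Day 2, 12:00 | 24 + 12 − 21 = +15 h |
| Day 2, 12:00 | Day 3, 12:00 | 48 + 12 − 21 = +39 h |
| Day 3, 12:00 | Day 4, 12:00 | 72 + 12 − 21 = +63 h |

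The day 1 discharge could be called as early as 12:00 that day, 9 hours before the dose. Men discharged after day 1 take the last dose in hospital, where bedside data collection continues.

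**3. Drug remaining.** Fifteen hours after the last dose, the fraction of that dose left is 0.5^(15/9) = 0.31 to 0.5^(15/15) = 0.50. This shows that exposure continues, not that events are missed.

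**4. Washout.** Five half-lives are 5 × 9 = 45 h to 5 × 15 = 75 h. From 21:00 on day 1, 75 hours ends at 00:00 on day 5. A day 4 call would fall inside the upper limit.

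**5. Scheduled observation after surgery.** This is at most stay plus 24 hours: 30, 48, 72 and 96 hours for assumed stays of 6, 24, 48 and 72 hours.

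**The case against.** A reader might infer that tamsulosin shortens stay, that its arm is therefore watched for less time, and that both the POUR and adverse-event comparisons lean toward it. The documents do not support this.

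- **POUR is normally settled in hospital.** Section 4.0 closes the endpoint at first void or catheterization, and the retention protocol in 6.5 calls for a bladder scan after 4 to 6 hours without voiding. If 4.0 governs, length of stay matters little.
- **The mechanism largely cancels itself.** The route to longer stay given in 1.0 is retention. Men kept in by retention already count as events in a yes/no outcome, so extra days add none. Bias would require shorter stay among men without an in-hospital event, and late events missed by both call and chart.
- **The direction for adverse events is open.** Drug effects such as hypotension could lengthen stay.
- **Rejection rates rest on invention.** With a true 17% in both arms and 264 per arm, missing 10% of events in one arm only (17.0% versus 15.3%) raises uncorrected rejection from 5% to 8.3%. Nothing in the documents supports a one-sided loss of that size.

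These objections stand. So does the point that scheduled contact is not the whole of observation. Chart review has no stated end, 9.2 implies some detection of readmissions and continued follow-up after serious drug-related events, and the diary card may document the last dose. The call topics are not said to be exclusive. The attached data sheet and DSMB plan are not in the text available and might define a window.

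The stake should also be kept in proportion. The uncovered dose is the seventh, after the 5 days that 2.0 gives for steady state. Section 9.1 puts orthostatic hypotension at 6% to 19% with the first dose but symptomatic cases below 1% in chronic therapy.

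None of this supplies a stated contact that asks about adverse events after the last home dose.

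**Conclusion.** The point holds as a gap in safety ascertainment. For day 0 discharges the call precedes the last dose except when discharge is later in the evening than the dosing hour. For day 1 discharges it comes before the dose or less than a day after it. Chart review and the diary card may recover part of what is missed, but chart review can miss symptoms at home.

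Scheduled active observation for adverse events therefore varies with length of stay. Neither the size nor the direction of any resulting bias can be derived from the documents, and the number of men affected is unknown. A biased POUR result is not shown. The open question there is which of 4.0 and 8.1 decides when the endpoint closes, and those sections must be reconciled. The change is worth making because 3.1 makes safety part of the primary objective and the remedy is cheap.

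**What to change.** 1. In 6.6, keep the routine 24-hour call and add a general adverse-event question for study patients.
2. Add one short scripted call on a fixed day counted from surgery, the same in both arms and after the last possible dose has washed out. With the protocol's half-life and an assumed 21:00 dose, that is postoperative day 5 or later. Ask about dizziness, fainting, falls, other adverse effects, readmission, any catheterization or emergency visit for retention, and whether the last dose was taken.
3. Make that day the end of the adverse-event window in 9.1 and the serious adverse-event window in 9.2, and run the planned chart review to the same day.
4. Reconcile 4.0 and 8.1 before applying any fixed window to POUR, since a new window would otherwise redefine the primary outcome and could conflict with 4.0. Until then, report post-discharge catheterization up to the fixed day separately.

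The cost is protocol wording and one short call per patient by nurses who already telephone them. Some calls will go unanswered, and the number should be reported by arm. The sample size is unchanged.

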7.0 Blinding

This is a double-blind study (i.e. the patient and investigators are both unaware of the specific study drug being administered).

Measures will be taken by the MMC Pharmacy to ensure tamsulosin and placebo are indistinguishable with regards to capsule shape, color and size. This will be done by inserting the tamsulosin capsule into a size 0 blue and white gelatin capsule (overlay), and formulating an identical capsule filled with lactose for the placebo.

In the event of a serious adverse event, the blind may be broken by contacting the study coordinator or principal investigator, who would in turn contact the pharmacy to determine whether the patient was on tamsulosin or placebo.

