9.2 Serious Adverse Events

Any event occurring while a patient is on study that meets the following criteria will be considered a Serious Adverse Event:

- Death
- Life-threatening (i.e. immediate risk of death)
- Readmission or prolongation of existing hospitalization
- Persistent or significant disability/incapacity

Important adverse events that may not result in death, may not be life –threatening, or do not require hospitalization may be considered serious when they may acutely jeopardize the patient without immediate medical attention to prevent one of the

outcomes listed above. Serious may also include any other event deemed as such by the investigator.

All serious adverse events will be monitored by clinical and/or research staff. The relationship of the adverse event to the study drug will be categorized as Not related, Unlikely to be related, Possibly related, Probably related and Definitely related. All serious adverse events will be reported to the IRB and DSMB within 5 days.

In the case of a serious drug-related adverse event, study drug will be discontinued and patients will continue to be followed.

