10.0 Analytic Methods

10.1 Data collection

Data will be collected prospectively by study staff in the office, at the bedside and through Epic chart review. A study ID will be assigned to each patient and study documents will all use this ID to collect data. Identifiable data will be stored separately. Baseline variables to be collected will include basic demographics, past medical history and medication list, PVR and IPSS. Operative data will include type and duration of surgery, fluid intake, medications given, and any perioperative urinary catheterization. Data will be recorded postoperatively will include fluid balance, need for urinary catheterization, pain medication and adverse events.

All data will be recorded on a data collection sheet (see attached data sheet). PVR and IPSS done in the MMP NSS office will also be recorded on separate forms (see attached PVR and IPSS forms), which will be linked to the primary data collection sheet. These data sheets will be stored in a locked and secure area of the study coordinator's office.

RedCap, a HIPAA-compliant database, will be used to store all information after it is collected. Data entry and access will only be allowed to research coordinator and Principal Investigator.

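### Does the code-break rule in section 7.0, which passes the treatment code through the roles that hold the database, put the trial's results at risk?

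*Combined protocol and SAP*

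**What the plan says.** Section 7.0 describes the blind as one in which "the patient and investigators are both unaware of the specific study drug being administered". Its single code-break rule is triggered by any SAE: "the blind may be broken by contacting the study coordinator or principal investigator, who would in turn contact the pharmacy" to learn the arm. The wording permits a break and does not require one. It does not say that the answer must bear on the man's care, does not ask for a log, and gives no route from the pharmacy directly to the treating clinician.

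Section 9.2 defines SAEs broadly. A lengthened stay counts, and so does anything the investigator considers serious. On handling it says "All serious adverse events will be monitored by clinical and/or research staff". On causality it says "The relationship of the adverse event to the study drug will be categorized as Not related", the first of five grades. No grader is named. On timing: "All serious adverse events will be reported to the IRB and DSMB within 5 days".

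Section 10.1 says of the database "Data entry and access will only be allowed to research coordinator and Principal Investigator", and of the source data "Data will be collected prospectively by study staff in the office, at the bedside and through Epic chart review".

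Three other provisions bear on the point. Section 6.2 has the pharmacy generate a 1:1 allocation without blocking. Section 6.3 blinds the whole care team. Section 6.5 puts bladder scanning and catheterization under the hospital's retention protocol.

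**The concern.** Read together, 7.0 and 10.1 look like a breach in the blind. The roles that obtain the code from the pharmacy are also the only ones that can enter or see data in the database. The trigger is wide, because section 1.0 itself links retention to a longer stay, and a longer stay is an SAE under 9.2. The event under study can therefore make a man eligible for a break.

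Two consequences would matter. First, an SAE could be graded for relatedness after the arm is known, since 9.2 does not require the grade to come first. An event in a man known to be on placebo would naturally be graded unrelated, so the distortion would have a direction, and section 3.1 makes adverse events part of the primary objective. Second, a man unblinded during preoperative dosing could still have surgery and count as evaluable under 10.2. His outcome could then be abstracted or entered by someone who knows his arm.

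**Working it through.** The plan gives no figure on this point to reproduce, so the check follows the code to each result the plan will report.

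**Who can learn the code.** The principal investigator is named in both 7.0 and 10.1. Section 7.0 says study coordinator where 10.1 says research coordinator, but 10.1 also uses the other title, and one role is probably meant. The overlap is real.

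**Other men.** Without blocking (6.2), one man's arm does not help to predict another's. The exposure stops at the men whose code is broken.

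**POUR.** The outcome in 8.1 is a catheterization or re-catheterization for acute retention. The volume threshold in 6.5 is a range, so there is discretion, but the blinded care team exercises it, not whoever enters the data. The database stores what has already been collected (10.1). Where a stay is lengthened by retention, POUR has occurred before any break. A preoperative break would precede the outcome, but the hospitalization criterion in 9.2 covers readmission or a longer stay and does not readily fit a man still at home. Such a break would need one of the other criteria. What is left is the abstraction of a few charts after a break.

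**Count of all SAEs.** A break needs an SAE to have been recognised, so the triggering event is identified before the arm is known. Only later events in the same man could be judged with that knowledge.

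**Length of stay and time to first void.** Both are timings taken from ward care. A clinician who asks for the code is unblinded under any code-break rule, so the route makes no difference to that.

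**Relatedness.** This is where a break could alter a judgment. The grade is not an outcome in 8.1 or 8.2, and 10.3 plans no analysis of it. Section 3.1 speaks of adverse events, not of events attributed to the drug.

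**The alternative route.** Suppose the pharmacy gave the code only to the treating clinician, on grounds of clinical need. Section 9.2 allows clinical staff to handle SAEs, so that clinician may be the grader. The documents do not say that the treating clinician and the principal investigator are different people, and 6.1 has attending surgeons taking consent for the study. The grade could still follow the break. The screening of requests by the coordinator or principal investigator would be lost, and whether the pharmacy can be reached at all hours is not documented.

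**Scale.** The documents give neither an SAE rate nor an unblinding rate. As an assumption only, if 1% to 5% of the 528 evaluable men (10.2) were unblinded:

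- 528 × 0.01 = 5.28, about 5 men
- 528 × 0.05 = 26.4, about 26 men

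These are men whose code would be known, not men whose data would be wrong. The conclusion does not rest on the range.

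**The case for a change.** The strongest case for an amendment is that the gap is real and cheap to close. Section 7.0 sets no criterion for a break, 9.2 stops study drug for a serious drug-related event without mentioning the code, and the pharmacy already holds the allocation. A clinical-need condition, a direct route and a one-page log would cost little, and a record of whether the grade and the outcome came before each break would let readers judge any remaining bias.

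Part of this stands. The text does allow a break for any SAE, and a grade given after a break is no longer blinded. Logging breaks, and recording the grade and any known POUR status before the code is released where feasible, is sound practice. Staff can do both under the present wording.

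The claim that rerouting the code removes the exposure does not stand. It moves the knowledge to another possible grader and neither names a blinded grader nor requires the grade first. The appeal to the primary objective also reaches too far, since relatedness enters no planned comparison.

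**Conclusion.** No change to the plan is needed. In the few cases where a code is broken, a role with database access may learn the arm, but no effect is shown on the POUR comparison, the count of all SAEs or the secondary outcomes. The exposure that remains is an unanalysed relatedness grade, and the alternative route would leave it in place. The choice between the two routes is a trade-off: the present one screens requests, while the other keeps the code from the data-handling roles but depends on a pharmacy service whose availability is not documented.

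This rests on three assumptions: that ward staff make the catheterization decision blinded, as 6.3 and 6.5 intend; that breaks are uncommon, which the documents neither support nor contradict with a rate; and that the attached DSMB plan and data sheet, which are not among these documents, do not give relatedness a larger role. Those attachments may also already contain grading or unblinding rules, so the plan cannot be said to lack them.

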8.0 Outcome

8.1 Primary Outcome

The primary outcome measure will be post-operative urinary retention, defined as the need for post-operative urinary catheterization for acute retention as defined by the MMC Acute Retention Protocol, or re-catheterization in those patients who leave the operating room with an indwelling catheter.

